#### Comments:

- Life-threatening in the definition of a SAE or SAR refers to an event in which the subject was at immediate risk of death at the time of event; it does not refer to an event which hypothetically might have caused death if it were more severe.
- Hospitalization means overnight admission.
- Hospitalization without underlying AE does not qualify as SAE. Examples are:
  - Hospitalization for protocol procedures e.g. chemotherapy.
  - Elective hospitalization for a pre-existing condition (i.e. a condition other than the indication for the chemotherapy) that has not worsened.
  - Hospitalization which was already planned at the beginning of the trial. Hospitalization must have been reported at screening visit in the source data and have been performed as planned.
  - Admission to a rehabilitation center or hospice.
  - Hospitalization for administrative or social reasons (e.g. due to anxiety but otherwise treatable on an outpatient basis).
- Medical and scientific judgement should be exercised in deciding whether expedited reporting is appropriate in other situations, such as important medical events that may not be immediately life-threatening or result in death or hospitalisation but may jeopardise the patient or may require intervention to prevent one of the other outcomes listed in the definition above. These should also usually be considered serious.

### 7.1.3 Adverse Drug Reaction (ADR)

All noxious and unintended responses to a medicinal product related to any dose should be considered ADRs.

The phrase "responses to a medicinal product" means that a causal relationship between a medicinal product and an AE is at least a reasonable possibility, i.e. the relationship cannot be ruled out.

### 7.1.4 Unexpected Adverse Reaction (UAR)

**Unexpected Adverse Reaction (UAR)** is an adverse reaction which does not meet any criteria for adverse reactions listed as known or possible side effects, neither in type nor in severity or outcome. The reference document for the assessment of expectedness is the current version of the Investigator's Brochure.

### 7.1.5 Serious Adverse Reaction (SAR)

**Serious Adverse Reaction (SAR)** is any harmful and unintended reaction possibly related to the study medication regardless of its dosage and which meets at least one of the SAE criteria mentioned above.

### 7.1.6 Suspected Unexpected Serious Adverse Reaction (SUSAR)

An adverse reaction, for which the nature, severity or outcome is not consistent with the applicable product information, which is serious according to definition in 7.1.2 and where the investigational product is suspected to be a contributor to the event.

## 7.2 Documentation of AEs and SAEs

AEs observed, mentioned upon open questioning by a member of the investigator team, or spontaneously reported by the subject, will be documented in the patient chart. AEs need also to be documented event based in the eCRF.

The investigator has to record all AEs occurring in the period between day 1 of study treatment (= enrolment) until 28 days after the end of venetoclax treatment on the respective eCRF pages. Patients will be followed-up for disease status and survival for minimum 24 months.

"Death" should not be reported as an SAE, since "death" is the outcome of the underlying SAE(s). The reason for the death should be reported as SAE.

For all SAEs, the investigator has to perform an assessment for seriousness and causal relationship to IMP.

## **7.3 Reporting of SAEs and SARs**

### **7.3.1 Reporting responsibilities of the investigator**

#### **SAEs**

All SAEs should be immediately reported by the investigator, i.e. within 24 hours after becoming aware of an event, which meets the definition of a SAE in 7.1.2. SAEs need to be reported to the sponsor's safety desk from day 1 of study treatment (= enrolment) until 28 days after last administration of study drug, regardless its causal relationship to the study drug.

If relevant information is missing at the time of the initial SAE report, the reporter should provide it in follow-up SAE report(s). Important follow-up information must also be reported as soon as they are available within 24 hours to the sponsor's safety desk. A follow-up report should contain new, updated or corrected information. The follow-up report should describe whether the event has resolved or continues, if and how it was treated including documentation of all supportive actions taken. Prompt notification (i.e. within 24h) of SAEs by the investigator to the sponsor's safety desk for SAE receipt is essential so that the legal obligations and ethical responsibilities towards the safety of the subjects are met. The investigator will comply with the applicable local regulatory requirements related to the reporting of SAE to CAs and ECs.

The investigator has to report any SAE immediately after the awareness in the AE/SAE section of the eCRF with all known and relevant information and has to sign and send the SAE page. The RELAX Safety Desk will be informed via Email about the occurrence of the SAE automatically.

In case the database does not work, the SAE has to be reported by fax or Email using the SAE form (sample in ISF).

RELAX Safety Desk, Medizinische Fakultät der TU Dresden, [contact], E-mail: [[contact]](mailto:[contact]) , [contact]

### **7.3.2 Reporting responsibilities of the sponsor**

#### **AEs**

The sponsor (or its representative) has to ensure that all AEs which occurred during the course of the study are properly documented. All reported AEs will be listed and discussed in respective reports (e.g. CSR). These reports are to be submitted to the competent authorities (CAs) and/or ethics committees (ECs) according to local requirements if requested.

#### **SAEs**

The sponsor will ensure that an SAE will be reported periodically to the relevant ECs and CAs in accordance with local site/country requirements.

## **SUSARs**

In accordance with national regulations and GCP guidelines, the sponsor should promptly notify all concerned investigators, institutions and the regulatory authorities of SUSARs and all findings that could affect adversely the safety of subjects, impact the conduct of the study or alter EC/CA approval to continue the study.

The sponsor (or its representative) has to report any reported SUSAR immediately, the latest within 7 days after notification for fatal and life-threatening SUSARs (with 8 days for follow-up), and within 15 days after notification for all other SUSARs to the relevant CAs, ECs and to the investigators.

### **Re-examination of the risk benefit profile**

The sponsor (or its representative) has to report immediately but the latest within 15 days after s/he got aware of the occurrence of any reason that requires a re-examination of the risk benefit profile of the study medication to the relevant ethical committee and the federal authorities (BfArM).

Included are:

- case reports of expected serious adverse reactions with an unexpected outcome,
- increase of the frequency of unexpected adverse reactions that are judged as clinical relevant,
- events that are related with the clinical study or the development of the study medication that can possibly affect the safety of the participant.

### **List of all SARs and safety report (Development Safety Update Report)**

The sponsor (or its representative) has to submit a list of SAR and a safety report to the relevant ethical committee and the federal authorities (BfArM) annually during the course of the clinical study or on request. The time frame for this report starts as soon as approval by the federal authority (BfArM) is available. The Sponsor (or its representative) will prepare these annual reports until the date of last patient last study visit, time points are defined in [section 3.7](#).

### **Measures to protect against imminent danger**

In case that the safety of the participants is impaired and the sponsor (or its representative) as well as the investigator take action to prevent the participants from any harm, the sponsor has to inform the relevant ethical committee and the federal authorities (BfArM) about these measures and causal circumstances.

## 8 Statistical analysis and sample size justification

### 8.1 Phase I - Dose escalation part

#### 8.1.1 Sample size

The dose escalation part of the trial is planned as 3+3 design. In the 3+3 design the sample size is determined by the number of dosing levels and the true probability of DLTs in the dosing levels. The study is planned with 4 dosing levels including one fallback safety dosing level. In case of observing 2 DLTs in dosing level 1 and 2 DLTs in dosing level -1 the minimum number of 4 patients will be treated in the dose escalation part. In case of 1 DLT in each dosing level the maximum number of 18 patients will be treated in this study part.

#### 8.1.2 Analysis set

##### 8.1.2.1 MTD analysis set

The analysis set for determination of the MTD will consist of all patients who experienced a DLT and all patients who received at least the minimum of the target dose of their cohort (see section [3.2.1](#)). Patients who did not complete DLT evaluation period due to reasons not comprising DLT will not be considered for determination of MTD and will be replaced.

##### 8.1.2.2 Safety evaluation set (SES)

All patients with exposure to venetoclax will be part of the safety evaluation set (SES).

#### 8.1.3 Definition of endpoint

##### 8.1.3.1 Primary endpoint maximum tolerated dose MTD

Maximum tolerated dose of cytarabine in combination with venetoclax plus mitoxantrone in the framework of a 3+3 design is the primary endpoint. It will be determined as described in section [3.2](#).

Additionally, a logistic regression model  $\text{logit}(P(\text{DLT}))=a+b*\text{cytarabine dose}$  will be fitted and an estimate for the MTD is derived by calculation of  $(\text{logit}(p_0)-a)/b$ . With  $p_0 = 0.33$  as the acceptable target toxicity level.

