### **3.2 Definition and determination of the maximum tolerated dose**

The combination of cytarabine and mitoxantrone plus venetoclax will be evaluated for tolerability in a 3+3 design. In a 3+3 design, three patients will form a cohort. Each cohort will receive a higher cumulative dose of cytarabine in the predefined dose escalation steps (see Table 1) in combination with a fixed dose of mitoxantrone and venetoclax. If one patient in a cohort experiences a DLT, the cohort will be expanded to 6 patients. If 0/3 or 1/6 patients in a cohort experience a DLT, the next dose escalation cohort will be opened. If two or more patients in a cohort experience a DLT, the next lower cytarabine dose will be defined as MTD. In case of  $\geq 2$  DLTs at the dose level 1, level -1 will be used as fallback option. In case of 0 or 1 DLT in the highest dose level, the MTD was not reached and this dose level will be defined as recommended phase-2 dose (RP2D).

The DLT evaluation period is defined as the first 28 days from the start of venetoclax treatment. If a patient has not recovered peripheral blood counts by day 28, the DLT evaluation period for hematologic toxicities will be extended until day 45 from start of V-MAC.

Note: If a DLT of TLS occurs during the lead-in period, it may affect dosing decisions in the ramp up period.

A DLT is defined as any of the following occurring events of a dose level and regarded to be probably or definitely related to venetoclax. The assessment is based on the question whether there was a “reasonable causal relationship” to venetoclax. Possible answers are “possible” or “unlikely”. An assessment of “unlikely” would include the existence of a clear alternative explanation, e.g. mechanical bleeding at surgical site or non-plausibility, e.g. the subject is struck by an automobile when there is no indication that the drug caused disorientation that may have caused the event.

Certain adverse events are likely to occur in the study population (AML) independent of drug exposure. Such events include known consequences of the underlying disease under

investigation (e.g. symptoms, disease progression). These events are listed in [Appendix 5](#). If not mentioned in Appendix, events with no reasonable causal relationship to venetoclax will not be considered as DLT. On the other hand, unlikely related events with unusually high occurrence during the trial could be considered DLT if agreed by the steering committee.

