### Cytarabine

Day 4-6 (10) 100 - 1000 mg/sqm (according to dose level)

Cytarabine will be given at increasing doses and should be administered after venetoclax intake. In the dose escalation part of the trial, cytarabine will be given at increasing doses as outlined in Table 1 starting from day 4. Cytarabine will be administered as continuous infusion in dose levels -1 and 1, by IV infusion over 2 hours twice daily in dose levels 2 and 3.

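### The supportive logistic MTD estimate in section 8.1.3.1 usually has no finite fit under the 3+3 rule, and when it has one it can land on a dose the rule has just rejected

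*Protocol*

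**What the plan says.** Protocol section 8.1.3.1 makes the MTD the phase I primary endpoint and refers to section 3.2 for its determination. It then adds, as a further analysis, the model logit(P(DLT)) = a + b × cytarabine dose, which "will be fitted and an estimate for the MTD is derived by calculation of" (logit(p0)-a)/b. The value p0 = 0.33 is described "as the acceptable target toxicity level". Section 8.1.4 makes the phase I analysis descriptive.

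The data come from the section 3.2 rule:
- Escalation: "If 0/3 or 1/6 patients in a cohort experience a DLT, the next dose escalation cohort will be opened".
- Stopping: "If two or more patients in a cohort experience a DLT, the next lower cytarabine dose will be defined as MTD".
- Fallback: with two or more "DLTs at the dose level 1, level -1 will be used as fallback option".

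On size, section 8.1.1 says: "The study is planned with 4 dosing levels including one fallback safety dosing level". It adds: "In case of 1 DLT in each dosing level the maximum number of 18 patients will be treated in this study part".

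On schedule, section 5.4.1 says: "Cytarabine will be administered as continuous infusion in dose levels -1 and 1, by IV infusion over 2 hours twice daily in dose levels" (the quote breaks off where the two higher levels are named). Levels -1 and 1 run over seven days, levels 2 and 3 over three. Table 2 ends venetoclax at day 10 at level -1 and at day 14 elsewhere.

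**The concern.** A logistic slope can be estimated only if patients with and without DLTs overlap along the dose axis. A 3+3 design works against this, because it stops at the first level with two or more DLTs and passes levels with none or one. The protocol fixes the model, the formula and p0, but gives no penalty, prior or fallback for separated data, no DLTs, or a slope at or below zero.

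Two further problems remain when a fit exists. First, p0 = 0.33 is called acceptable, whereas 2/6 (33%) at a level puts that level above the MTD in section 3.2. Second, the dose in the model could be per infusion, per day or cumulative. Section 3.2 escalates on cumulative dose, but section 8.1.3.1 does not say which is meant, and the levels differ in infusion mode and days. A value between levels 1 and 2 matches no defined schedule.

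At stake is a second MTD figure, printed beside the primary endpoint, that may be missing, uninformative or at odds with it.

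**Working it through.** **Inputs.** The rule is from section 3.2, the formula and p0 from 8.1.3.1, and the doses from Table 1. Cumulative cytarabine is 100×7 = 700, 200×7 = 1400, 500×2×3 = 3000 and 1000×2×3 = 6000 mg/m2 for levels -1, 1, 2 and 3. The protocol gives no true DLT rates, so these are assumptions. Ordinary maximum likelihood is also an assumption, being the default reading of a fitted logistic model.

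**The plan's own figures.** Six patients at each of levels 1 to 3 gives 3×6 = 18, the stated maximum. Two DLTs in two patients at level 1 and again at level -1 gives 4, the stated minimum. Both reproduce, and neither yields an estimate:
- 1/6, 1/6, 1/6 has the same observed rate at every level, so b = 0 and the formula divides by zero.
- 2/2 and 2/2 contains only DLTs, so no finite fit exists.

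**How often a finite fit exists.** The fit is finite only if the highest dose with a DLT-free patient exceeds the lowest dose with a DLT, and the highest dose with a DLT exceeds the lowest dose with a DLT-free patient. The rule, with cohorts completed in threes, has 73 possible outcome tables. Each was checked and weighted by its exact binomial probability. The no-DLT column can be verified by hand. For the first curve, (0.95×0.90×0.80)^3 = 0.684^3 = 0.32.

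| Assumed DLT % at levels 1/2/3 (level -1) | No DLT | DLTs only at highest level tried, some patients there DLT-free | Finite fit | Positive slope, estimate within tested doses |
|---|---|---|---|---|
| 5/10/20 (3) | 32% | 41% | 23% | 7% |
| 10/20/30 (5) | 13% | 53% | 30% | 17% |
| 15/30/45 (10) | 4% | 60% | 32% | 25% |
| 10/25/50 (5) | 4% | 61% | 29% | 24% |

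The remaining few percent per row are other non-finite patterns.

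Over a wider grid of 715 non-decreasing curves with rates from 2% to 60%, the probability of no finite fit has median 72% and range 43-94%, and it exceeds 50% in 96% of curves. A positive-slope estimate within the tested doses arises in at most 30% of trials (median 20%). Existence was the same for all three dose codings checked (per-dose, daily and cumulative).

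**What the ratio does when DLTs occur only at the highest level tried.** If some patients there are DLT-free, a and b diverge but (logit(p0)-a)/b tends to that dose, whatever fraction had DLTs. The number simply returns the last dose tried.

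**Conflict with the 3+3 rule.** Take 1/6 at level 1 and 2/6 at level 2. The 3+3 MTD is level 1 (1400 mg/m2 cumulative). For the model:
- logit(1/6) = ln(1/5) = -1.6094 and logit(2/6) = ln(1/2) = -0.6931.
- b = (-0.6931 + 1.6094)/(3000 - 1400) = 0.9163/1600 = 0.00057268.
- a = -1.6094 - 1400 × 0.00057268 = -2.4112.
- logit(0.33) = -0.7082.
- Estimate = (-0.7082 + 2.4112)/0.00057268 = 2974 mg/m2.

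That is essentially the 3000 just rejected. On daily dose it is 987 against 1000. With 0/3, 1/6, 2/6 the 3+3 MTD is level 2, and the model gives 5809 against the rejected 6000.

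A level with a true 33% DLT rate passes the rule with probability 0.67^3 + 3×0.33×0.67^2×0.67^3 = 0.301 + 0.134 = 0.43, so the rule turns such a level away more often than not.

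**The case against.** The strongest reply is that nothing depends on this number. Section 8.1.3.1 determines the MTD by section 3.2 and introduces the model only as an addition, section 8.1.4 makes phase I descriptive, and phase II uses the MTD or highest tolerable dose from escalation. This stands in full. A reader might infer that the phase I primary endpoint fails, or that no rule says which MTD counts. The protocol supports neither.

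Second, maximum likelihood is not named. A SAP could specify a penalised or Bayesian fit of the same model without contradicting the text. A Firth-penalised fit has a finite positive slope in 90-98% of trials over five rising curves, although the estimate lies within the tested doses in only 27-91%. So the formula usually fails under the default fit, but it is not bound to fail.

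Third, it is tempting to call the estimate undefined whenever the data are separated. In the commonest pattern the ratio has a limit. It is uninformative rather than undefined.

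Fourth, section 3.2 declares the MTD not reached with 0 or 1 DLT at the highest level, so a missing estimate is then expected. The protocol's 18-patient case is one of these. Such trials make up 63%, 31%, 9% and 9% of the non-finite cases under the four curves. This softens the first two rows of the table but leaves about 91% of the non-finite cases in the last two.

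Fifth, p0 can be read as the boundary at which the rule stops, since the rule acts on observed counts and p0 is a model probability. That explains the choice, but the formula then estimates the dose at that boundary while section 3.2 takes the level below it. Finally, nothing says that an interpolated dose would be given to patients.

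**Conclusion.** The point holds for a supportive, descriptive analysis. As written, with an ordinary fit, the formula gives finite coefficients in about 23-32% of trials and a positive-slope estimate within the tested doses in about 7-25%. These figures rest on the four assumed DLT curves and on maximum likelihood. The wider grid shows that the conclusion does not hang on those curves; the exceptions are curves with about 33% or more DLTs already at level 1. The divergence from the 3+3 MTD follows from the protocol's own p0 and stopping rule. The undefined dose variable matters less numerically: for 1/6, 0/3, 2/6 the estimate moves only from 1.07 to 1.13 times level 3 across codings. It still leaves the reported figure without a stated unit. The 3+3 MTD and the phase II dose decision are unaffected.

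**What to change.** In section 8.1.3.1, or in the SAP as section 8.1.4 allows, replace the unpenalised fit and the interpolated dose by one of these:
- isotonic (pool-adjacent-violators) DLT rates at each dose level actually used, with exact intervals; this exists for every 3+3 outcome and needs no dose metric;
- a penalised or weakly informative Bayesian logistic model, reporting the DLT probability at the actual levels only.

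If a model is kept, state whether dose means per infusion, daily or cumulative mg/m2, and acknowledge that schedule and, at level -1, venetoclax duration change with it. Reconcile p0 = 0.33 with the section 3.2 treatment of 2/6; which of the two should move is for the sponsor to decide.

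The cost is a few lines of text and minor programming. The Bayesian option also needs a stated prior, whose influence on so few patients should be shown.

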#### 8.1.4 Statistical methods

The analysis of the phase I trial part will be of descriptive nature. It will be based on the first treatment cycle. Further treatment cycles will not be considered for determination of MTD. Changes to the analyses, specified in this protocol, will be described in a detailed statistical analysis plan.

#### **8.1.4.1 Descriptive statistics**

All study variables will be presented using appropriate descriptive statistics. For all variables the absolute numbers and percentages of non-missing and missing values will be presented. Calculated statistics for the different variable types will be as follows:

- continuous variables: arithmetic mean, standard deviation, median, interquartile range, minimum and maximum will be presented
- categorical variables: absolute number and percentage

#### **8.1.5 Analysis of safety**

Descriptive analysis of safety and toxicity will be conducted in the SES.

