#### **4.4.2 Replacement**

Subjects who experience a DLT will NOT be replaced.

In the dose escalation part of the trial (i.e. phase I), following patients should be replaced to ensure the required number of evaluable subjects per cohort:

- subjects not experiencing a DLT who have taken less than the required study treatment as described in section [3.2.1](#)
- subjects with incomplete DLT evaluation period due to any reason other than a DLT even if they have received the required study treatment (section [3.2.1](#))

In the expansion part of the trial (i.e. phase II), subjects will not be replaced.

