##### **8.1.5.2 Dose limiting toxicities (DLT)**

All dose limiting toxicities will be listed separately per dose level, including description of the event, date of first administration of cytarabine, date of first administration of venetoclax, date of last administration of cytarabine drug, date of last administration of venetoclax, date of onset of AE, date of end of AE, severity, seriousness, relatedness to either venetoclax or cytarabine, action taken and outcome

Incidences of DLTs will be reported with counts and percentage grouped by CTCAE toxicity grade, dose level, severity, outcome, related study drug and overall.

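### Section 8.1.5 places the phase I DLT percentages in the safety evaluation set, so a replaced, venetoclax-exposed patient lowers the reported rate wherever a DLT has occurred

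*Protocol*

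**What the plan says.** Section 8.1.5 (Analysis of safety, phase I) opens with a single rule for everything beneath it: "Descriptive analysis of safety and toxicity will be conducted in the SES". Section 8.1.5.2, directly under it, requires: "Incidences of DLTs will be reported with counts and percentage grouped by CTCAE toxicity grade, dose level, severity, outcome, related study drug and overall". It states no denominator of its own.

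Section 8.1.2.2 defines the phase I SES as all patients exposed to venetoclax, with no condition on how much treatment they received or how long they were observed.

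Section 8.1.2.1 defines a second set, for determination of the MTD. It consists of "all patients who experienced a DLT and all patients who received at least the minimum of the target dose of their cohort". Patients whose DLT evaluation period was incomplete for a reason other than a DLT "will not be considered for determination of MTD and will be replaced". Section 4.4.2 gives the matching replacement rule. Patients with a DLT are not replaced. Those replaced are "subjects not experiencing a DLT who have taken less than the required study treatment", and those without a DLT whose evaluation period was cut short. The minimum treatment that makes a patient evaluable is set in section 3.2.1.

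**The concern.** A DLT percentage is meant to describe patients in whom a DLT could have been observed under adequate treatment and follow-up. The protocol says who those patients are and builds a set for them. It then directs the DLT percentages to a wider set that also holds patients it has declared not evaluable. Counting such a patient in the denominator treats an unobserved outcome as an observed absence of DLT.

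Any resulting error has one direction: the dose level looks safer. The percentage printed for a level could then differ from the fraction on which escalation was decided. Section 3.1 says that safety and tolerability data from the escalation part go to the competent authority and ethics committee in support of the recommended phase II dose. The protocol does not say that the DLT table is part of that submission, but a DLT summary is a natural component of it and should agree with the decision it supports.

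**Working it through.** **The plan's own figures.** Section 8.1.1 gives a maximum of 18 and a minimum of 4 patients. Three levels (1, 2, 3) × 6 = 18, and 2 DLTs at level 1 plus 2 at level -1 gives 2 + 2 = 4. Both reproduce, and neither allows for replaced patients. The protocol states no DLT rate, so there is no percentage to reproduce.

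**Inputs.**
- Cohort size 3, expanded to 6 after one DLT; 0/3 or 1/6 allows escalation, and two or more DLTs stop it (section 3.2).
- Acceptable target toxicity level 0.33 (section 8.1.3.1).
- Replaced patients carry no DLT (section 4.4.2).
- Number of replaced, exposed patients per level, r: not stated. I assume 1 to 3.

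**Formula.** With d DLTs among n evaluable patients, the MTD analysis set gives d/n and the SES gives d/(n + r). Since r ≥ 0, d/(n + r) ≤ d/n. The inequality is strict only if d ≥ 1 and r ≥ 1. The relative understatement is r/(n + r).

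| DLTs / evaluable | MTD analysis set (same as SES if r = 0) | SES, r = 1 | SES, r = 2 | SES, r = 3 |
|---|---|---|---|---|
| 0/3 or 0/6 | 0% | 0% | 0% | 0% |
| 1/6 | 16.7% | 14.3% | 12.5% | 11.1% |
| 2/6 | 33.3% | 28.6% | 25.0% | 22.2% |
| 2/3 | 66.7% | 50.0% | 40.0% | 33.3% |
| 3/18 (overall) | 16.7% | 15.8% | 15.0% | 14.3% |

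In the overall row, r is the total across levels. For n = 6 the relative understatement is 1/7 = 14%, 2/8 = 25% and 3/9 = 33%. A level with 2/6 DLTs, which fails the 3+3 rule, sits at the 0.33 target in the MTD analysis set and at 28.6% in the SES after one replacement.

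**Can replacement happen?** At levels 1 to 3 the planned venetoclax total is 50 + 100 + 200 + 11 × 400 = 4750 mg (section 5.4.1). Three missed 400 mg doses leave 4750 − 1200 = 3550 mg, below the 3800 mg minimum of section 3.2.1. Section 5.4.1 provides for withholding venetoclax when laboratory changes suggest tumor lysis, so the route exists. If each treated patient has an assumed probability q of needing replacement, the chance that a six-patient level has none is (1 − q)^6:

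| q (assumed) | 5% | 10% | 20% | 30% |
|---|---|---|---|---|
| No replacement among six | 73.5% | 53.1% | 26.2% | 11.8% |

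An undiluted rate is therefore quite possible at a given level, and so is a diluted one.

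**The case against.** The strongest reply is that little depends on these percentages. Escalation and the MTD follow counts in evaluable cohorts (sections 3.2 and 8.1.2.1), so the protocol already uses the right set where evaluability matters. Section 8.1.4 calls the phase I analysis descriptive. Section 8.1.5.2 also asks for counts and a listing of every DLT, and in cohorts of three to six most readers look at the counts. A shift from 16.7% to 14.3% is 2.4 points, against an exact 95% interval for 1/6 of about 0.4% to 64%. All of this stands, and it limits the severity.

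Three further arguments carry less weight.
- Reporting toxicity in all exposed patients is an accepted convention. That holds for adverse events, but DLT status has its own evaluability definition in this protocol.
- Several groupings in 8.1.5.2, such as grade or outcome, may be shares of events rather than of patients. That leaves the by-dose-level and overall percentages as they are.
- Section 8.1.4.1 requires missing values to be reported, which could make non-evaluable patients visible. It does not say that they leave the denominator.

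The SES is inherited from the parent section rather than repeated in 8.1.5.2. It is nevertheless the only set named for this analysis, so the protocol has not left the choice open.

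A reader might infer that every reported DLT rate is biased, or that the dose decision is compromised. The documents support neither. A rate moves only where a DLT and a replaced, exposed patient both occur. The MTD is determined in a different set. Nor does the protocol present the DLT percentage as the principal phase I result: its phase I primary endpoint is the MTD.

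**Conclusion.** Wrong as written, minor severity. Followed literally, section 8.1.5 puts replaced patients into the denominator of the DLT percentages, and the effect can only be downward. One assumed replacement at a six-patient level lowers 16.7% to 14.3% or 33.3% to 28.6%. The largest case shown for a six-patient level, a 33% relative understatement, needs three replacements there. These sizes rest on assumed replacement numbers, because the protocol gives none. The direction does not rest on them: it follows from the replacement rule. The harm is confined to descriptive reporting.

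**What to change.** In section 8.1.5.2, state that DLT percentages by dose level and overall are computed in the MTD analysis set of section 8.1.2.1. Next to the DLT table, list the replaced patients per dose level with the reason for replacement. Keep the SES for exposure, adverse event and laboratory summaries. A DLT figure based on the SES may be added as a labelled supplement.

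The cost is one sentence, in the protocol or as a documented change in the statistical analysis plan, and one short listing. No further data collection is needed beyond the withdrawal reasons already recorded under section 4.4.1. The only downside is that the reported DLT percentages may be slightly less favourable.
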